4.10 Duration of Follow Up

Patients removed from study treatment for unacceptable adverse events will be followed until resolution or stabilization of the adverse event. Patients will be followed after removal from study treatment every 28 days (+/-7 days) for 8 visits, then every 56 days (+/- 7 days) until death, lost to follow-up, withdrawal of consent, or initiation of subsequent therapy for disease progression (see Section 5 for assessments).

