DURATION OF INVESTIGATIONAL AGENT ADMINISTRATION AND STUDY PARTICIPATION

Duration of UC-961 administration is until disease progression, treatment intolerance, or lack of clinical benefit. Patients may remain on the clinical trial protocol until one of the following:

- Clinical or radiographic progressive disease (See Section 12).
- Adverse Events requiring removal from study (See Section 13).
- Refusal of further protocol therapy by patient/parent/guardian
- Non-compliance that in the opinion of the investigator does not allow for ongoing participation.
- Physician determines it is in the patient's best interest to discontinue participation in the clinical trial.
- Completion of all clinical trial procedures.

	Participation in the study and long-term follow-up will continue until one of the following:
	Death.
	Loss to follow-up.
	Withdrawal of consent for any further data submission.
	Progression requiring initiation of subsequent therapy.
	UC-961 is administered by intravenous infusion on day 1, 15, 29, 43, 57, 85, 113, and 141, after which responses will be assessed.
STUDY DRUG ADMINISTRATION	Patients with an objective response (meeting working group criteria for partial response or complete response) will continue at the same dose and schema. Patients with stable disease or progressive disease are eligible to increase the dose of UC-961 for another 6-month course.
CRITERIA TO EVALUATE SAFETY	Safety will be determined by Principal Investigator, and will be assessed according to the NCI Common Terminology Criteria for Adverse Events version 4.03 (NCI CTCAE v4.03) for non-hematologic toxicity and modified iwCLL criteria for hematologic toxicity.
CRITERIA TO EVALUATE EFFICACY	Overall response rate is the percentage of patients meeting criteria for partial response, nodular partial response, or complete response based on iwCLL criteria. Progression free survival is according to iwCLL definition.

Completed UC-961 Phase 1 Clinical Trial (UC-961 q 14 days x 4 doses)

Screen for eligibility for UC-961 Extension Trial

- √ Tolerated UC-961 without dose limiting toxicity and recovered from toxic effects to grade 1 or baseline.
- √ If intervening CLL therapy, maintains measurable disease.

UC-961 q 14 days x 4 doses, then q 28 days x 4 doses (dose based on ongoing phase 1 trial)

Response assessment (labs, imaging, bone marrow biopsy)

Repeat UC-961 course (dose increase if PD or SD)

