2.5 Secondary Endpoints

- **2.5.1** Overall response rate by IWCLL criteria following 6 months of biweekly dosing of UC-961 (Hallek *et al.*, 2008)
- **2.5.2** Progression free and overall survival (progression determined by IWCLL working group criteria)
- 2.5.3 SD, PR, and MRD- rates, as well as individual components of response (reduction in leukemia count, reduction in adenopathy and splenomegaly, and improvement in BM function), as determined by IWCLL working group criteria.

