4.0 INVESTIGATIONAL TREATMENT PLAN

4.1 Dose Assignment

The dose of UC-961 is currently undergoing evaluation in a phase 1 study.

During the extension treatments, patients will be assigned to receive the highest safe dose from an ongoing phase 1 study, or the established maximum tolerated dose/ recommended phase 2 dose (which may increase as the phase 1 trial accrues additional patients). Patients will receive the same dose of UC-961 for 1 course, which consists of 8 doses (every 14 days for 4 doses, then every 28 days for 4 doses). As of April 2016, the highest safe dose is 8 mg/kg.

Following 1 course, patients will be assessed for response, and then are eligible to receive a second course. Patients with a complete response or partial response will continue at the same

dose. Patients with stable disease or progressive disease will receive a higher dose of UC-961, if a higher safe dose has been established in the concurrent CLL Phase 1 trial by that time.

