4.11 Criteria for Removal from Study

Patients can be taken off the study at any time at their own request, or they may be withdrawn at the discretion of the investigator for safety, behavioral or administrative reasons. The reason(s) for discontinuation will be documented and may include:

- a) Death.
- b) Loss to follow-up.
- c) Withdrawal of consent for any further data submission.
- d) Disease progression requiring initiation of subsequent therapy.

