5.5 Long term follow-up

Every 28 days (+/- 7 days) for 8 visits then every 56 days (+/- 7 days), until discontinuation of trial participation:

- **5.5.1** Complete history and physical examination including vital signs (blood pressure, heart rate, temperature, weight) and organ measurements (i.e., lymph nodes, spleen, liver).
- **5.5.2** Adverse events grading and reporting.
- **5.5.3** Standard laboratory examinations: hematology (CBC w/differential), comprehensive metabolic panel (Na+, Cl-, K+, CO2, BUN, Creatinine, Glucose, Ca2+, total protein, albumin, total bilirubin, SGPT, SGOT, alkaline phosphatase), phosphorous, magnesium, uric acid, LDH.
- **5.5.4** Collection of correlative lab samples.

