7.2.1 Progression-Free Survival

Progression-free survival (PFS) is defined as the duration of time from start of treatment until objective tumor progression or death.

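### Overall survival is a secondary endpoint, but follow-up stops at next therapy for progression and no later vital-status check is planned, so the planned curve would not be overall survival

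*Combined protocol and SAP*

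**What the plan says.** Section 2.5.2 lists "Progression free and overall survival (progression determined by IWCLL working group criteria") as a secondary endpoint, and section 2.2.1 presents it as new relative to the initial phase 1 trial. Section 10.0 plans median survival estimates, Kaplan-Meier plots and 95% confidence intervals, all descriptive.

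Four places govern when follow-up ends:

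- Section 4.10 continues visits "until death, lost to follow-up, withdrawal of consent, or initiation of subsequent therapy for disease progression".
- The synopsis, on duration of participation, states "Participation in the study and long-term follow-up will continue until one of the following" and includes in its list "Progression requiring initiation of subsequent therapy".
- Section 4.11 gives "Disease progression requiring initiation of subsequent therapy" among the possible reasons for removal from the study.
- Section 5.5 runs long-term follow-up visits "until discontinuation of trial participation".

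In the schedule of events (6.0), long-term follow-up is the last column, and there is no row or column for survival status. Section 7.2.1 gives a definition for the companion endpoint: "Progression-free survival (PFS) is defined as the duration of time from start of treatment until objective tumor progression or death". There is no counterpart for OS.

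**The concern.** OS counts deaths from any cause, including those after progression and later treatment. Here observation stops when a patient progresses and needs new treatment. That event is tied to prognosis, so the patients leaving the risk set cannot be assumed to have the same death risk as those who stay. A Kaplan-Meier curve built on these data is valid for OS only if they do.

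The direction of any bias depends on the death hazard after next therapy compared with before it. The curve is too high if the later hazard is higher, correct if the two are equal, and too low if next therapy lowers the hazard or goes to fitter patients. The documents do not settle which applies, and the data to be collected could not show it. Even with no bias, events and precision are lost.

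**Working it through.** **Is any other route to later deaths planned?**

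- Deaths after progression but before new therapy are captured, because follow-up continues until new therapy starts.
- Deaths during a second on-study course are also captured. Section 4.1 allows this course even after progression: "Patients with stable disease or progressive disease will receive a higher dose of UC-961", if a higher safe dose has been established.
- Section 8.6.1 covers serious adverse events during the study or within 30 days of the last dose. This is a safety window.
- Section 8.1 monitors existing adverse events until they resolve or are explained, or until death. It does not track survival.
- Section 5.7.2 has a medical-record review, but for banked specimens and with no schedule.

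None of these is planned survival follow-up.

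**Size.** The plan has no OS figure to reproduce: no rate, event count or follow-up length. The following is an illustration.

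Inputs:

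- Death hazard before next therapy: a = 0.06 per year (assumed).
- Hazard of next therapy: m = ln 2 / median time to it. A 12-month median gives m = 0.693 per year (assumed).
- Ratio of death hazard after to before next therapy: h = 0.5, 1, 2 or 4 (assumed).
- Horizon t = 2 years; exponential times; no other censoring (assumed).
- n = 33, the anticipated enrolment in the synopsis.

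Formulas:

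- Curve censored at next therapy: exp(−at) = exp(−0.12) = 88.7%.
- True OS: exp(−(a+m)t) + m[exp(−hat) − exp(−(a+m)t)] / (a+m−ha).
- Deaths collected: a/(a+m) × [1 − exp(−(a+m)t)] = 0.0797 × (1 − 0.2217) = 6.2% of patients.

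For example, with h = 2: 0.2217 + 0.693 × (0.7866 − 0.2217) / 0.633 = 84.0%.

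| h | True 2-year OS | Planned curve | Bias (points) | All deaths | Share not collected |
|---|---|---|---|---|---|
| 0.5 | 91.2% | 88.7% | −2.5 | 8.8% | 30% |
| 1 | 88.7% | 88.7% | 0 | 11.3% | 45% |
| 2 | 84.0% | 88.7% | +4.7 | 16.0% | 61% |
| 4 | 75.8% | 88.7% | +12.9 | 24.2% | 74% |

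For the same four ratios, the bias is −3.6, 0, +6.7 and +18.4 points with a 6-month median to next therapy, and −1.5, 0, +2.8 and +7.9 with a 24-month median. A simulation of 1,000,000 patients per ratio at the 12-month median agreed with the closed form.

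**Precision when h = 1 (no bias).**

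- Patients still followed at 2 years: 33 × 0.2217 = 7.3.
- Greenwood variance, planned follow-up: 0.887² × [a/(n(a+m))] × [exp((a+m)t) − 1] = 0.887² × 0.0797 × 3.51 / 33 = 0.00667. The 95% half-width is 1.96 × √0.00667 = 16.0 points.
- Complete follow-up: 1.96 × √(0.887 × 0.113 / 33) = 10.8 points.

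**The case against.** - **OS carries little weight here.** This is a single-arm extension with a safety aim, no hypothesis test is planned, and OS drives no decision. This stands and limits the severity.
- **The size is entirely assumed, and the death rate is held at 6% per year.** This also stands. With a 12-month median and h = 2, the bias is +1.7 points at 2% per year and +7.9 at 12% per year. At 2% per year, only about 0.7 deaths before next therapy would be seen among 33 patients by 2 years.
- **The bias is smaller than the noise.** With 33 patients this holds in every scenario above: 4.7 against a half-width of 16.0 points, and 18.4 against 25.4 at the extreme. But part of that width is caused by the censoring itself, and bias does not shrink with enrolment. At the synopsis maximum of 75 patients, the half-widths become 16.0 × √(33/75) = 10.6 and 25.4 × √(33/75) = 16.8, below the h = 4 biases of 12.9 and 18.4.
- **Some later deaths could still be recorded** through the 30-day safety window, adverse event monitoring or the specimen record review. They could, but only incidentally. The accurate statement is that later deaths are not systematically collected.
- **The censoring date is inferred, and PFS has no censoring rule either.** Both are true. The inference follows from when contact ends, and the missing PFS rule does not repair OS.

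**Conclusion.** The concern holds. The synopsis and sections 4.10, 4.11 and 5.5 consistently end observation at next therapy for progression, and nothing later in the plan restores survival data. Reported as OS, the planned estimate would be survival censored at a prognosis-linked event. Under the assumptions stated (6% deaths per year before next therapy, median 6 to 24 months to next therapy, hazard ratio 0.5 to 4), the 2-year bias runs from −3.6 to +18.4 points, and it is zero only when the hazards are equal. At the 12-month median, equal hazards still mean that 45% of 2-year deaths are missed and that the interval is about half as wide again (16.0 / 10.8 = 1.5). The fault is in the follow-up rule and does not depend on these rates. It should be fixed, but it touches only one descriptive secondary result; the safety analysis is unaffected.

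**What to change.** In the synopsis, sections 4.10, 4.11 and 5.5, and the schedule in 6.0, separate the end of clinic visits from survival follow-up. After next therapy starts, record its date and the date of death or last known alive, by chart review or telephone. Continue until death, loss to follow-up, withdrawal of consent for further data, or a stated cut-off date.

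In sections 7.2 and 10.0, define OS as time from start of treatment to death from any cause, censored at the date last known alive and not at next therapy.

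If this follow-up is not wanted, replace OS with time to next therapy or death, or label the estimate as survival censored at next therapy and state the limitation.

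The cost is a protocol amendment, brief chart or telephone contacts, and possibly consent wording; the consent form was not available to check. No visits, procedures or patients are added. The OS figure may turn out less favourable. The change is best made early, since contact is hard to recover once patients have left the study.

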4.11 Criteria for Removal from Study

Patients can be taken off the study at any time at their own request, or they may be withdrawn at the discretion of the investigator for safety, behavioral or administrative reasons. The reason(s) for discontinuation will be documented and may include:

- a) Death.
- b) Loss to follow-up.
- c) Withdrawal of consent for any further data submission.
- d) Disease progression requiring initiation of subsequent therapy.

5.0 STUDY PROCEDURES

5.1 Screening/Baseline Procedures

Assessments performed exclusively to determine eligibility for this study will be done only after obtaining informed consent. Assessments performed for clinical indications (not exclusively to

determine study eligibility) may be used for baseline values even if the studies were done before informed consent was obtained.

All screening procedures must be performed within 30 days prior to Cycle 1 Day 1 of the study unless otherwise stated. The screening procedures include:

- **5.1.1** Complete history and physical examination including vital signs (blood pressure, heart rate, temperature, weight) and organ measurements (i.e., lymph nodes, spleen, liver).
- **5.1.2** Current medications will be recorded in the subject's medical record but not captured in case report forms.
- **5.1.3** 12 lead ECG. ECG is required on screening. Subsequent ECG will be performed during the study as clinically indicated.
- **5.1.4** Laboratory examinations: hematology (CBC w/differential), comprehensive metabolic panel (Na+, Cl-, K+, CO2, BUN, Creatinine, Glucose, Ca2+, total protein, albumin, total bilirubin, SGPT, SGOT, alkaline phosphatase), phosphorous, magnesium, uric acid, LDH, amylase, lipase.
- **5.1.5** Coagulation parameters: PT/PTT.
- **5.1.6** If female of child-bearing potential: serum pregnancy test within 14 days of Cycle 1 Day 1.
- **5.1.7** Subjects will have bone marrow aspirate and biopsy with samples sent for differential, morphology, and flow cytometry for MRD within 90 days prior to Cycle 1 Day 1, so long as there has been no intervening CLL therapy.
- 5.1.8 Disease staging to include CT, MRI, and/or PET scan as clinically indicated (typically including chest, abdomen, pelvis to measure non-palpable lymph nodes) within the last 60 days prior to Cycle 1 Day 1 if there has been no intervening CLL treatment. Any appropriate radiological and radioisotope examinations should be performed as clinically indicated.
- **5.1.9** Research Tests: peripheral blood and serum collection for one or more of the following (i) Leukemia cell immunophenotype, (ii) T and B cell immune response, (iii) plasma cytokine levels. (see Correlative Studies Section 5.9).

5.2 UC-961 Extension Course 1:

UC-961 doses are administered on Days 1, 15, 29, 43, 57, 85, 113, and 141; all +/- 3 days). The following are to be completed on the day of each infusion.

- **5.2.1** Complete history and physical examination including vital signs (blood pressure, heart rate, temperature, weight) and organ measurements (i.e., lymph nodes, spleen, liver).
- **5.2.2** Current medications will be recorded in the subject's medical record but not captured in case report forms.
- **5.2.3** Adverse events assessment and grading per patient reporting.
- **5.2.4** Standard laboratory examinations: hematology (CBC w/differential), comprehensive metabolic panel (Na+, Cl-, K+, CO2, BUN, Creatinine, Glucose, Ca2+, total protein, albumin, total bilirubin, SGPT, SGOT, alkaline phosphatase), phosphorous, magnesium, uric acid, LDH. Also: amylase; lipase.

- **5.2.5** Collection of PK samples.
- **5.2.6** Collection of correlative lab samples.
- **5.2.7** If criteria met for start of cycle (section 4.5), proceed with pre-medications (section 4.3) and UC-961 infusion (dose per section 4.1; infusion procedure per section 4.4)
- **5.2.8** Post-infusion monitoring: patients will be observed for at least 1 hour following the infusion of UC-961, with continued measurement of blood pressure, pulse, temperature every 30 minutes (+/- 10 minutes).
- **5.2.9** Peripheral blood draw 1 hour after the end of the infusion (+/- 10 minutes), including comprehensive metabolic panel (CMP), phosphorous, uric acid, LDH.

5.3 Day 169 +/- 7 days: Response Assessment:

Not all activities are required on the same day.

- **5.3.1** Complete history and physical examination including vital signs (blood pressure, heart rate, temperature, weight) and organ measurements (i.e., lymph nodes, spleen, liver).
- **5.3.2** Adverse events grading and reporting.
- **5.3.3** Standard laboratory examinations: hematology (CBC w/differential), comprehensive metabolic panel (Na+, Cl-, K+, CO2, BUN, Creatinine, Glucose, Ca2+, total protein, albumin, total bilirubin, SGPT, SGOT, alkaline phosphatase), phosphorous, magnesium, uric acid, LDH. Also: amylase; lipase.
- **5.3.4** Collection of correlative lab samples.
- **5.3.5** Flow cytometry of peripheral blood for T-cell subtypes and CLL MRD.
- **5.3.6** CT scan or MRI or PET of chest, abdomen, and pelvis.
- **5.3.7** Bone marrow biopsy if clinically indicated to evaluate complete response / minimal residual disease.

5.4 UC-961 Extension Course 2:

UC-961 doses are again administered every 14 days for the first 4 doses, then every 28 days for 4 doses (Days 197, 211, 225, 239, 253, 281, 309, 337; all \pm 7 days).

- **5.4.1** Complete history and physical examination including vital signs (blood pressure, heart rate, temperature, weight) and organ measurements (i.e., lymph nodes, spleen, liver).
- **5.4.2** Current medications will be recorded in the subject's medical record but not captured in case report forms.
- **5.4.3** Adverse events assessment and grading per patient reporting.
- **5.4.4** Standard laboratory examinations: hematology (CBC w/differential), comprehensive metabolic panel (Na+, Cl-, K+, CO2, BUN, Creatinine, Glucose, Ca2+, total protein, albumin, total bilirubin, SGPT, SGOT, alkaline phosphatase), phosphorous, magnesium, uric acid, LDH. Also: amylase; lipase.
- **5.4.5** Collection of PK samples.

- **5.4.6** Collection of correlative lab samples.
- **5.4.7** If criteria met for start of cycle (section 4.5), proceed with pre-medications (section 4.3) and UC-961 infusion (section 4.4)
- **5.4.8** Post-infusion monitoring: patients will be observed for at least 1 hour following the infusion of UC-961, with continued measurement of blood pressure, pulse, temperature every 30 minutes (+/- 10 minutes).
- **5.4.9** Peripheral blood draw 1 hour after the end of the infusion (+/- 10 minutes), including comprehensive metabolic panel (CMP), phosphorous, uric acid, LDH.

5.5 Long term follow-up

Every 28 days (+/- 7 days) for 8 visits then every 56 days (+/- 7 days), until discontinuation of trial participation:

- **5.5.1** Complete history and physical examination including vital signs (blood pressure, heart rate, temperature, weight) and organ measurements (i.e., lymph nodes, spleen, liver).
- **5.5.2** Adverse events grading and reporting.
- **5.5.3** Standard laboratory examinations: hematology (CBC w/differential), comprehensive metabolic panel (Na+, Cl-, K+, CO2, BUN, Creatinine, Glucose, Ca2+, total protein, albumin, total bilirubin, SGPT, SGOT, alkaline phosphatase), phosphorous, magnesium, uric acid, LDH.
- **5.5.4** Collection of correlative lab samples.

5.6 Pharmacokinetic (PK) Studies

Serum samples will be banked for analysis. HPLC–based assay used in antibody production will also be utilized for serum antibody levels. Limited PK studies are planned, with collection of serum **prior to and 1 hour after** each dose of UC-961.

Sample Collection and Handling Instructions

Blood samples (up to 10 ml) will be collected in heparinized tubes at a site distant from the infusion for pharmacokinetic evaluation. Samples cannot be drawn from the 2nd lumen of a multi-lumen catheter through which drug is being administered. The exact time that the sample is drawn along with the exact time that the drug is administered should be recorded.

Sample Processing: Plasma will be isolated in the translational laboratory ([name]) and stored at minus 20 degrees.

Sample Labeling

Each tube must be labeled with the patient's de-identified study number, and the date and time the sample was drawn. Data should be recorded on the Pharmacokinetic Study Form, which must accompany the sample(s).

Sample Shipping Instructions

Samples may be shipped to third-party vendor for PK analysis. Samples will be shipped as per assay manufacturer recommendations.

5.7 Correlative Studies

Studies will be performed in the [name] laboratory, to correlate with PK and clinical responses. Samples will be taken at baseline/screening, during treatment and after treatment. However, not all assays will be performed for all time points for all patients, based on sample availability and leukemic cell number. Specimens will be banked in the CLL research consortium tissue repository (see below).

Assays from patient serum may include:

- Measurement of cytokine levels (IL2, IL12, and TNFα) and Wnt5a levels.
- Assessment for anti-UC-961 antibody production.

Isolation of leukemic cells by Ficoll-hypaque separation and assessment, which may include:

- UC-961 antibody binding, ROR1 expression and receptor occupancy
- ZAP-70, CD38, and Immunoglobulin heavy chain variable region (IgVH) mutation in CLL cells
- Assessment of down-stream signaling by multiplex qPCR
- Measurement of Akt and phospho-Akt levels prior to and after therapy.
- Expression of co-stimulatory molecules (CD80 and CD86), apoptosis related receptors (CD95 and DR5), and expression of genes and proteins related to apoptosis, from pre-treated and post-treated samples.

